informed consent, each subject will receive 10 mg/kg of oral valacyclovir, and may start taking oral valacyclovir while still in the birth hospital, with subsequent dosing at home, or may start taking oral valacyclovir following discharge from the birth hospital. **Study Day 1** is the day that the first dose of oral valacyclovir is administered. Following signing of informed consent but prior to administration of the first dose of valacyclovir, hematology and chemistry safety labs (white blood cell count and differential for absolute neutrophil count, hemoglobin, platelet count, alanine aminotransferase, and creatinine) will be obtained and values checked; if no baseline hematology or chemistry values are Grade 1 toxicity or higher then dosing of valacyclovir will proceed; if any value is Grade 1 toxicity or higher, the subject will be withdrawn from the study prior to receiving any doses of study medication. In addition, the subject must have had a first void before receiving a first dose of study medication. A single plasma sample will also be obtained for a baseline acyclovir concentration, since the mothers of enrolled subjects will have been taking antiviral medication prior to delivery. Dropouts and withdrawn subjects may be replaced to reach the target sample size of eight subjects. Subjects will return to the study site on Study Day 5 (window: Study Day 4 through Study Day 5), and also will be assessed for adverse events and concomitant medications on Study Day 10 (window: Study Day 7 through Study Day 13) and on Study Day 42 (window: Study Day 35 through Study Day 49), although the Study Day 10 and 42 assessments may occur via telephone or in-person study visits. On the Study Day 5 (window: Study Day 4 through Study Day 5) visit, plasma samples for PK assessments will be obtained around dose 7, 8, 9, or 10 of study drug at 0 hour minus 15 minutes (pre-dose), and then 1-2 hours, 4-6 hours, and 8-10 hours following administration of the valacyclovir dose (full PK profile). Safety laboratory assessments (white blood cell count with differential, hemoglobin, platelet count, alanine aminotransferase, and creatinine) will be obtained at the Study Day 1 (baseline) and Study Day 5 visits. Safety laboratory values will be classified using the Division of AIDS Toxicity Tables ([Appendix A](#)). Study drug will be stopped following the obtaining of the PK samples on Study Day 5 (window: Study Day 4 through Study Day 5). Criteria for AEs or SAEs leading to halting of the study are detailed in [Section 7.1.1](#). The total number of study days of study drug administration will be 4 or 5 (depending on where in the window the Study Day 5 visit is conducted), although the total number of doses can be 7, 8, 9, or 10 depending upon when the study drug was started on Study Day 1 and whether the PK blood draws on Study Day 5 (window: Study Day 4 through Study Day 5) are around the first or second dose that day.

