The breakdowns of the amount of blood for individual tests are provided in the Schedule of Activities in [Section 1.2](#). Clinical laboratory results can be used for chemistry and hematology safety labs if collected within the required study window. If labs drawn for the study-required assessments are not evaluable, blood draws will not be repeated.

Hematology Safety Labs

All hematology safety laboratory assessments will be conducted at the PI's local lab. They will be obtained on Study Days 1 and 5. The following will be tested: white blood cell count (WBC)

with differential, hemoglobin, and platelet count. From the WBC count and differential, the absolute neutrophil count (ANC) will be calculated (39).

Chemistry Safety Labs

All chemistry safety laboratory assessments will be conducted at the PI's local lab. They will be obtained on Study Days 1 and 5. The following will be tested: alanine aminotransferase (ALT) and creatinine.

Special Assays or Procedures: Pharmacokinetic Testing

Assessment of acyclovir plasma concentrations will be conducted at the UAB Central Pharmacokinetic Laboratory. On Study Day 1, a blood sample will be obtained at the same time as the Study Day 1 hematology and chemistry safety labs. On Study Day 5 (window: Study Day 4 through Study Day 5), blood will be obtained around dose 7, 8, 9, or 10 of study drug at 15 minutes before the dose (pre-dose), and then 1-2 hours, 4-6 hours, and 8-10 hours following administration of the dose. Specific instructions for shipping PK samples are found in the MOP.

8.3.1 Procedures to be Followed in the Event of Abnormal Laboratory Test Values or Abnormal Clinical Findings

If a physical parameter or laboratory value is outside of the protocol specified range, then the measurement may be repeated if there is a technical problem with the measurement caused by a laboratory error or a malfunctioning or inappropriate device. Laboratory parameters other than those specified in hematology safety labs and chemistry safety labs as part of the CBC and complete metabolic panel need to be evaluated by the site physician, recorded in the source document, and reported as laboratory AEs if clinically significant.

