9.4.4 Safety Analyses

Safety evaluations will be based on the incidence, severity, and type of AEs. Safety variables will be tabulated and presented for all subjects in the safety population. All tests will use a 5% significance level, i.e., p-values < 0.05 will be considered significant, and for estimation a 95% confidence level will be used.

Symptoms and toxicities will be listed and the counts and proportion computed by dose cohort. Clopper-Pearson method will be used to estimate confidence intervals (or upper bound) around the estimates of these proportions and Fisher's exact test to compare the proportions between dose cohorts. Summary statistics will be presented for continuous laboratory safety parameters. Data will be presented using appropriate graphical tools to help compare the different dose cohorts. The exact Wilcoxon test will be used to compare between dose cohorts at a given time point or area under the curve for variables collected over time (e.g., laboratory parameters). For area under the curve, the average will be taken to adjust for shortened length of follow-up for dropouts. Linear mixed model with random intercept may be considered to analyze data collected over time to account for correlation of data from the same subject. This method provides another perspective of comparing the treatment cohorts as area under the curve due to being a summary statistic may miss important features of the data that mixed model may detect. The generalized linear mixed model can handle continuous, binary and count data. To measure strength of correlation between continuous variables, the Pearson correlation (or Spearman rank correlation for variables not distributed normally) will be used. Analyses will be done using SAS version 9.4.

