6.5. Missing Data

Missing safety data will be assumed to be missing completely at random and will not be imputed.

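### The laboratory area-under-the-curve comparison between cohorts averages one pre-dose and one on-drug value, so it halves any Day 5 difference and lets in pre-dose imbalance

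*Protocol*

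**What the plan says.** Protocol 9.4.4 states: "The exact Wilcoxon test will be used to compare between dose cohorts at a given time point or area under the curve for variables collected". The sentence ends by naming repeated laboratory measurements as the example. The protocol adds: "For area under the curve, the average will be taken to adjust for shortened length of follow-up for dropouts". Protocol 9.4 carries the same two sentences. On the error rate, 9.4.4 says "All tests will use a 5% significance level". Protocol 9.4.1 makes the Wilcoxon test two-tailed and applies no multiplicity adjustment.

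Haematology and chemistry safety labs are "obtained on Study Days 1 and 5" (Protocol 8.3). The first draw comes "prior to administration of the first dose of valacyclovir, hematology and chemistry safety labs" being taken and checked at that stage (Protocol 4.1), so it is a baseline. No other safety draw is scheduled.

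No formula for the area is given, nor a minimum number of values. The SAP's laboratory section (9.6) plans severity by time point, descriptive statistics and change from baseline. It contains neither a laboratory area under the curve nor a between-cohort test. SAP section 1 nevertheless says the document covers all planned safety analyses, and section 15 reports no change to them.

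**The concern.** A time-averaged area is a sensible summary when several post-dose values are available. With one pre-dose and one on-drug value it becomes their simple mean. The safety question is whether the on-drug value differs between 10 and 20 mg/kg. The mean of the two draws answers a different question, because half of it was fixed before the first dose.

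Two consequences follow. A real Day 5 difference is diluted. A pre-dose difference between cohorts can also produce a significant result by itself. Such a difference is plausible here: the cohorts are enrolled one after the other without randomisation, infants enter at up to 2 days of age, and the protocol's Appendix A moves the upper end of the Grade 1 neutrophil band from 5,000 at 1 day or less to 1,500 at 2 to 7 days. Baseline neutrophil counts may therefore depend on age at the draw. Neutropenia and raised creatinine are the two risks that Protocol 2.3.1 names.

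The averaging rule is meant to handle dropouts, but it gives no usable value for an infant who has only the baseline result.

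**Working it through.** **The plan's own figures.** No power or effect size is stated for this test. The sample-size figures that are stated reproduce for n = 8: 1 − 0.025^(1/8) = 0.3694; 24,000 ± t(0.975, 7) × 8,000/√8 gives 17,312 to 30,688; 48,000 with SD 15,998 gives 34,625 to 61,375. None of them bears on the laboratory comparison.

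**Inputs.** From the documents: two draws, the first pre-dose; 8 infants per cohort; two-tailed exact Wilcoxon at 5%. Not in the documents, so assumed: normal values, a Day 5 shift of d SDs, Day 1/Day 5 correlation ρ from 0 to 0.7, and equal SDs (then varied).

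**Step 1: what the statistic is.** With values Y1 and Y5 a time L apart, the trapezoid area is L(Y1 + Y5)/2. Divided by L it is (Y1 + Y5)/2, whatever L is. For values 10 and 4: 21/3 = 7.0 over 3 days and 28/4 = 7.0 over 4 days.

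**Step 2: dilution.** A Day 5 difference of d becomes d/2. The SD of the average is √((1 + ρ)/2). The standardised effect relative to Day 5 alone is therefore 1/√(2(1 + ρ)): 0.71, 0.62, 0.58 and 0.54 at ρ = 0, 0.3, 0.5 and 0.7. It is below 1 for every ρ above −0.5.

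If the baseline SD is half the Day 5 SD, the variance of the average is (0.25 + 1 + ρ)/4 and its standardised effect is d/√(1.25 + ρ). At d = 1.5 that is 1.34 for ρ = 0 and 1.07 for ρ = 0.7, so less is lost.

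**Step 3: power.** The exact 8 v 8 test rejects when U ≤ 13 or U ≥ 51 (exact size 0.0499). Simulation with 40,000 trials per setting, d = 1.5:

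| ρ | Day 5 value | Averaged area, equal SDs | Averaged area, baseline SD half |
|---|---|---|---|
| 0 | 77% | 49% | 68% |
| 0.3 | 77% | 39% | 59% |
| 0.5 | 77% | 35% | 54% |
| 0.7 | 77% | 31% | 49% |

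With equal SDs and ρ = 0.5, a 1-SD shift gives 44% on Day 5 against 18% on the averaged area; a 2-SD shift gives 95% against 55%.

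**Step 4: pre-dose imbalance with no dose effect.** Suppose the cohorts differ by 1 SD at baseline.
- If the difference has gone by Day 5, the averaged-area test rejects 25% to 17% of the time (ρ = 0 to 0.7). The Day 5 test stays at 5%, which that assumption guarantees.
- If the difference carries forward by the factor ρ, the averaged area rejects about 31% to 39% of the time at ρ = 0.3 to 0.7, and the raw Day 5 test about 8% to 24%.
- In the second case the expected Day 5 difference is ρ × 1. Adjustment at the true slope removes ρ × 1, leaving 0.

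With no baseline difference, both tests keep their 5% level.

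**Step 5: baseline result only.** Area divided by follow-up is 0/0. If the average instead means the mean of available values, it is Y1 alone. Under that second reading, with d = 1.5, ρ = 0.5 and equal SDs, one or two such infants among the 8 in the higher-dose cohort lower power from 35% to 27% or 20%. The counts of one and two are assumed.

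**The case against.** The strongest reply is that this test may never be run. The SAP has no laboratory area and no between-cohort laboratory test, so no planned table would carry the problem. The protocol sentence also offers a single time point as the alternative, Protocol 9.4.1 describes the laboratory comparison at a time point only, and 9.4.4 itself concedes that an area summary can miss features and mentions a mixed model. All of this limits the impact. It does not remove the option: the protocol text stands in two sections, nothing says which alternative applies, and the SAP drops the tests without declaring a change.

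A reader might infer three stronger things that the documents do not support.

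- **That infants without an on-drug lab are counted as unaffected treated infants.** This is one reading of an undefined rule. The case is also narrower than dropout in general: Protocol 7.2 asks for next-visit labs on the day of discontinuation if possible and allows replacement, and SAP 3.3 lets unscheduled results fill a time point. It can still occur, because Protocol 8.3 says non-evaluable labs are not redrawn and puts chemistry last when blood is short. Nor does the pre-dose check guarantee a normal baseline. It requires no value of Grade 1 or higher, and the SAP's abnormal-result listings separate out-of-range results from graded ones.
- **That the averaging rule contradicts SAP 6.5**, which says "Missing safety data will be assumed to be missing completely at random and will not be imputed". Averaging observed values is not imputation, and the SAP has no laboratory area for that rule to govern.
- **That drug toxicity would be missed.** Individual and study halting rules (Protocol 7.1), graded laboratory events and abnormal-value listings do not use this test, and neither does the Cohort 2 dose decision (Protocol 9.4.6).

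**Conclusion.** The concern holds as a minor correction. That the averaged area is half pre-dose value follows from the visit schedule alone and needs no assumption. Smaller power than Day 5 alone follows, with equal SDs, for any correlation above −0.5.

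The size does rest on assumptions, since the documents give no laboratory SDs, correlations or effect sizes. At a 1.5-SD effect the loss is about 28 to 46 percentage points with equal SDs (77 − 49 to 77 − 31) and about 9 to 28 points if the baseline SD is half (77 − 68 to 77 − 49). The smaller loss deserves weight, because excluding infants with a Grade 1 or higher baseline value may narrow the baseline spread.

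The raw Day 5 comparison is better but does not solve baseline imbalance when the imbalance persists, so it should not stand alone.

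**What to change.** In Protocol 9.4 and 9.4.4, delete the area-under-the-curve option and the averaging rule for laboratory parameters.

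If a between-cohort comparison is kept, use the Day 5 value in infants with an on-drug result, with a baseline-adjusted Day 5 comparison beside it. Plain change from baseline is a weaker choice when the correlation is low: at ρ = 0 and 1.5 SD its power is 49%, no better than the averaged area, against 77% at ρ = 0.5. Show the number of infants without an on-drug result by cohort; the SAP's summary-statistics shells already count infants with data at each time point.

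Then reconcile the two documents. Either add the comparison to SAP 9.6 or state that none will be made, and record the change in SAP section 15.

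The cost is wording and at most one small table, with no new data or infants. The downside is that the comparison may have fewer than 8 infants per cohort, and the baseline slope would be estimated from at most 16.

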9.4.5 Baseline Descriptive Statistics

Baseline characteristics will be summarized. For both continuous and categorical variables, appropriate summary statistics will be applied. For continuous variables, descriptive statistics will include the number of non-missing values, mean, standard deviation, median, minimum, and maximum. For categorical variables, descriptive statistics will include counts and percentages per category.

9.4.6 Planned Interim and Early Analyses

The initial oral valacyclovir dose will be 10 mg/kg administered two times daily for 5 days (**Cohort 1**). The target exposure for acyclovir following oral valacyclovir dosing is 36,000 ngxhr/mL with a range of 24,000 ngxhr/mL to 48,000 ngxhr/mL. Upon full accrual of Cohort 1, the PK and safety data will be reviewed. If the mean of observed acyclovir exposures of subjects in Cohort 1 are below 24,000 ngxhr/mL, AND if no Grade 3 or Grade 4 AEs or SAEs are detected in any of the study subjects, then the 8 subjects enrolled in Cohort 2 will receive oral valacyclovir at a dose of 20 mg/kg administered two times daily for 5 days. Alternatively, if the mean of observed acyclovir exposures of subjects in Cohort 1 are above 48,000 ngxhr/mL AND if no Grade 3 or Grade 4 AEs or SAEs are detected in any of the study subjects, then the 8 subjects enrolled in Cohort 2 will receive oral valacyclovir at a dose that has been linearly adjusted downward to target 36,000 ngxh/mL area-under-the-concentration-time curve from 0 to 12 hours (AUC_{12}). The SMC retains the ability to suggest an alternative dose be studied in Cohort 2 if the mean AUC_{12} from Cohort 1 is within but at or near the lower or upper ranges in order to attain an AUC_{12} closer to the 36,000 ngxhr/mL target. After assessment of drug exposure and safety in Cohort 1, eight new subjects will be enrolled in **Cohort 2**, with the dose that these subjects will receive being predicated upon the pharmacokinetic data from Cohort 1.

If the targeted exposure is not achieved in Cohorts 1 and 2 and the safety data are acceptable, it is possible, but not anticipated, that additional dosing cohorts could be recommended based upon the results of subjects in the first two cohorts. If such a recommendation is made, dose selection and subject enrollment and assessment will follow the approach used for Cohort 2.

9.4.6.1 Interim Safety Analyses

See [Section 9.4.6](#).

9.4.6.2 Interim Immunogenicity or Efficacy Review

Not Applicable

9.4.7 Sub-Group Analyses

Not Applicable

9.4.8 Tabulation of Individual Participant Data

Individual participant data will be listed by measure of pharmacokinetic parameter, including demographic characteristics.

9.4.9 Exploratory Analyses

Not applicable

10. SUPPORTING DOCUMENTATION AND OPERATIONAL CONSIDERATIONS

10.1 Regulatory, Ethical, and Study Oversight Considerations

Ethical Consideration

This trial will be conducted in compliance with the protocol, International Conference on Harmonization Good Clinical Practice E6 (ICH-GCP), and the applicable regulatory requirements, including:

- U.S. Code of Federal Regulations applicable to clinical studies (45 CFR 46 and 21 CFR including parts 50 and 56 concerning informed consent and IRB regulations, if under IND, 21 CFR 312).
- Completion of Human Subjects Protection Training.

The investigator will ensure that this study is conducted in full conformity with the principles set forth in The Belmont Report: Ethical Principles and Guidelines for the Protection of Human Subjects of Research of the US National Commission for the Protection of Human Subjects of Biomedical and Behavioral Research (April 18, 1979) and codified in 45 CFR Part 46 and/or the ICH E6; 62 Federal Regulations 25691 (1997).

Institutional Review Board

The UAB Central Unit will identify the IRB that will serve as the Single (Central) IRB of record for the U.S. sites participating in this study. Only institutions holding a current US Federalwide Assurance (FWA) issued by OHRP will be allowed to participate in this study.

This protocol, informed consent documents, relevant supporting information, and all types of volunteer recruitment or advertisement information will be submitted to the Single IRB of record for review and must be approved before the study is initiated. Any amendments to the protocol must also be approved by the Single IRB of record prior to implementing changes in the study. The UAB Central Unit will inform the Single IRB of record of the progress of the study and of any changes made to the protocol as deemed appropriate, but at least once per year.

The site investigator is responsible for keeping their local IRB apprised of the progress of the study and of any changes made to the protocol as deemed appropriate, but at least once per year. All IRB approved documents as well as relevant study correspondence should be copied and sent to the UAB Central Unit.

10.1.1 Informed Consent Process

The process of obtaining informed consent must be documented in the medical records, clinic chart, and/or research chart. The consent form must be signed and dated by the subject's parent(s)/legal guardian(s) before participation in the study. A copy of the signed consent form must be provided to the subject's parent(s)/legal guardian(s). Signed consent forms must remain

in each study participants study file and must be available for verification by study monitors at any time.

The investigational nature and research objectives of this study, its procedures, and its attendant risks and discomforts will be carefully explained to the subject's parent(s)/legal guardian(s). A signed informed consent document will be obtained from each subject's parent(s)/legal guardian(s) prior to entry into this study. At any time during participation in the protocol, if new information becomes available relating to risks, this information will be provided orally or in writing to all enrolled or prospective subject's parent(s)/legal guardian(s). Documentation will be provided to the IRB and, if necessary, the informed consent will be amended to reflect any relevant information.

An investigator shall seek such consent only under circumstances that provide the subject's parent(s)/legal guardian(s) sufficient opportunity to consider whether or not to participate and that minimize the possibility of coercion or undue influence. The information that is given to the subject's parent(s)/legal guardian(s) shall be in language understandable to the subject's parent(s)/legal guardian(s).

The subject's parent(s)/legal guardian(s) will sign the informed consent document prior to any procedures being done specifically for the study. The subject's parent(s)/legal guardian(s) should have the opportunity to discuss the study with their family, friends or personal physician, or think about it prior to agreeing to participate. The subject's parent(s)/legal guardian(s) may withdraw consent at any time throughout the course of the study. A copy of the informed consent document will be given to the subject's parent(s)/legal guardian(s) for their records. The rights and welfare of the subjects will be protected by emphasizing to them that the quality of their medical care will not be adversely affected if they decline to participate in this study.

10.1.1.1 Requirements for Permission by Parents/Guardians and Assent by Children (in case of a minor)

If required by the IRB, the parent or legal guardian will sign a waiver of assent for the minor due to the study participant's age.

10.1.1.2 Other Informed Consent Procedures

Not applicable

10.1.2 Study Termination and Closure

The NIH or study Principal Investigator have the right to terminate this study at any time. Reasons for terminating the study may include, but are not limited to, the following:

- The incidence or severity of adverse events in this or other studies indicates a potential health hazard to study participants.
- Study participant enrollment is unsatisfactory.
- Data recording is inaccurate or incomplete.
- Investigators do not adhere to the protocol or applicable regulatory guidelines in conducting the study.
- Regulatory authority action.

The sponsor will notify regulatory authorities as applicable.

